### **9.3 Study stopping rules**

#### **Overall study stopping rules:**

If any of the following occur within a cohort, enrollment in the study within that cohort will be placed on hold, and no new participants may be dosed, however enrollment and dosing in any other concurrently running cohorts without safety concerns may continue.

- One or more study-treatment related SAEs
- Two or more similar SAEs, regardless of suspected drug-relatedness
- Two or more participants experience hypersensitivity reactions or injection reactions of moderate to severe intensity
- Two or more participants experience a similar AE, which was assessed as severe in intensity, and are considered as potentially related to the study treatment
- The Sponsor considers that the number and/or severity of AEs, abnormal safety monitoring tests or abnormal laboratory findings justify putting the study on hold

The study may resume following the safety review, if the Investigators and Sponsor agree it is safe to proceed.

### **9.4 Study completion and post-study treatment**

Cohort completion is defined as when the last participant finishes their End of Cohort (EOC1 and/or EOC2) visit and any repeat assessments associated with this visit have been documented and followed-up appropriately by the Investigator or, in the event of an early cohort termination decision, the date of that decision.

Study completion is defined as when the last participant of the final cohort of the study finishes their End of Cohort (EOC1 and/or EOC2) visit and any repeat assessments associated with the visit has been documented and followed-up appropriately by the Investigator or, in the event of an early study termination decision, the date of that decision.

For participants who discontinue the study early and do not return for the Early Termination Visit (see [Section 8](#)), a safety follow-up call will be conducted 30 days after last administration of study treatment.

The information collected is kept as source documentation. All SAEs reported during this time period must be reported as described in [Section 10.1.3](#) and the SOM. Documentation of attempts to contact the participant should be recorded in the source documentation.

### **9.5 Early study termination by the sponsor**

The study can be terminated by Novartis at any time for any reason. This may include reasons related to the benefit/ risk assessment of participating in the study, practical reasons (including slow enrollment), or for regulatory or medical reasons. In taking the decision to terminate, Novartis will always consider the participant welfare and safety. Should early termination be

necessary, participants must be seen as soon as possible and treated as a prematurely withdrawn participant. The investigator may be informed of additional procedures to be followed in order to ensure that adequate consideration is given to the protection of the participant's interests. The investigator or sponsor depending on the local regulation will be responsible for informing IRBs/IECs of the early termination of the trial.

## **10 Safety monitoring and reporting**

### **10.1 Definition of adverse events and reporting requirements**

#### **10.1.1 Adverse events**

An adverse event (AE) is any untoward medical occurrence (e.g., any unfavorable and unintended sign [including abnormal laboratory findings], symptom or disease) in a participant or clinical investigation participant after providing written informed consent for participation in the study. Therefore, an AE may or may not be temporally or causally associated with the use of a medicinal (investigational) product.

The investigator has the responsibility for managing the safety of individual participant and identifying adverse events.

Novartis qualified medical personnel will be readily available to advise on trial related medical questions or problems.

The occurrence of adverse events must be sought by non-directive questioning of the participant at each visit during the study. Adverse events also may be detected when they are volunteered by the participant during or between visits or through physical examination findings, laboratory test findings, or other assessments.

Adverse events must be recorded under the signs, symptoms, or diagnosis associated with them, accompanied by the following information (as far as possible) (if the event is serious refer to [Section 10.1.2](#)):

1. The severity grade will be used to characterize the severity of the Adverse Events based on the this general guideline:
  - mild: usually transient in nature and generally not interfering with normal activities
  - moderate: sufficiently discomforting to interfere with normal activities
  - severe: prevents normal activities
2. Its relationship to the study treatment and investigational PET CCI radioligand. If the event is due to lack of efficacy or progression of underlying illness (i.e. progression of the study indication) the assessment of causality will usually be 'Not suspected.' The rationale for this guidance is that the symptoms of a lack of efficacy or progression of underlying illness are not caused by the trial drug, they happen in spite of its administration and/or both lack of efficacy and progression of underlying disease can only be evaluated meaningfully by an analysis of cohorts, not on a single participant
3. Its duration (start and end dates or ongoing) and the outcome must be reported
4. Whether it constitutes a SAE (see [Section 10.1.2](#) for definition of SAE) and which seriousness criteria have been met

5. Action taken regarding with study treatment

All adverse events must be treated appropriately. Treatment may include one or more of the following:

- Dose not changed
- Drug interrupted/permanently discontinued

6. Its outcome

Conditions that were already present at the time of informed consent should be recorded in medical history of the participant.

Adverse events (including lab abnormalities that constitute AEs) should be described using a diagnosis whenever possible, rather than individual underlying signs and symptoms.

Adverse event monitoring should be continued for at least 30 days (or 5 half-lives or end of study visit, whichever is longer) following the last dose of study treatment.

Once an adverse event is detected, it must be followed until its resolution or until it is judged to be permanent (e.g., continuing at the end of the study), and assessment must be made at each visit (or more frequently, if necessary) of any changes in severity, the suspected relationship to the interventions required to treat it, and the outcome.

Information about adverse drug reactions for the investigational drug can be found in the Investigator's Brochure (IB).

Abnormal laboratory values or test results constitute adverse events only if they fulfill at least one of the following criteria:

- They induce clinical signs or symptoms
- They are considered clinically significant
- They require therapy

Clinically significant abnormal laboratory values or test results must be identified through a review of values outside of normal ranges/clinically notable ranges, significant changes from baseline or the previous visit, or values which are considered to be non-typical in participants with the underlying disease.

Instructions are outlined in the SOM for data capture methodology regarding AE collection for participants that fail screening.

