#### **4.5 Rationale for Study Follow-up Period**

All participants receiving treatment in this study should have safety evaluations and collection of concomitant treatments and/or adverse event data until the predefined end of cohort date for each investigational agent. Please refer to [Section 9.1.1](#) for details pertaining to early study discontinuation and associated safety follow-up.

For monoclonal antibodies, and other biologic agents with a long half-life, the end of cohort completion visit (EOC2) will be extended to day 281. The rationale for extending this is based on the following: 1) the typical half-life of a monoclonal antibody is approximately four weeks, 2) assuming monthly dosing of the monoclonal antibody, the duration of time between last dose on week 20 and EOC2 is 20 weeks, and 3) 20 weeks would be approximately 5 half-lives after last dose, which is the longest duration of safety observation expected to be required of any agent to be included in the study.

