**Table 8-1 Assessment Schedule**

Commercially Confidential Information

Inclusion / Exclusion criteria	X	X										
Physical Examination/Neurological Examination	S		S	S		S		S	S	S	S	
Smoking and alcohol history	S											
Alcohol Test and Drug Screen	S											
Pregnancy and assessments of fertility	S	S		S		S		S	S	S	S	S
Hepatitis and HIV Screen	S											
Tuberculosis test	S											S
Demography	X											
Medical history/current medical conditions	X	X	X			X		X	X	X	X	X

Period	Screening		Treatment								End of Cohort		Safety Follow-Up		
Visit Name	Screening	Baseline	Initial Dose Day	Step-Up Visit		Treatment	Step-Up Visit	Treatment		End of Cohort Visit (EOC1) for All Molecules	End of Cohort Visit (EOC2) for Large Molecules Only - Extended Safety Visit	Early Termination Visit (Only when discontinuation from treatment/study occurs. See Section 9.)			
Days	-60 to -8	-7 to -1	1	8 ±1	15 ±1	22 ±1	29 ±2	36 ±1	57 ±2	85 ±3	113 ±2	141 ±2	171 -0 +2	281 ±2	30 days post last dose
Body Height	X														
Vital signs and body measurements	X	X	X	X	X	X	X	X	X	X	X	X	X	X	
AEs/SAEs	X	X	X	X	X	X	X	X	X	X	X	X	X	X	
Concomitant medications	X	X	X	X	X	X	X	X	X	X	X	X	X	X	
Electrocardiogram (ECG)	X		X	X					X			X	X	X	
Blood collection CCI	X														
Hematology	X	X		X		X		X	X	X	X	X	X	X	
Clinical Chemistry	X	X		X		X		X	X	X	X	X	X	X	
Urinalysis	X	X		X		X		X	X	X	X	X	X	X	

Commercially Confidential Information

Period	Screening		Treatment								End of Cohort		Safety Follow-Up		
Visit Name	Screening	Baseline	Initial Dose Day	Step-Up Visit		Treatment	Step-Up Visit	Treatment		End of Cohort Visit (EOC1) for All Molecules	End of Cohort Visit (EOC2) for Large Molecules Only - Extended Safety Visit	Early Termination Visit (Only when discontinuation from treatment/study occurs. See Section 9.)			
Days	-60 to -8	-7 to -1	1	8 ±1	15 ±1	22 ±1	29 ±2	36 ±1	57 ±2	85 ±3	113 ±2	141 ±2	171 -0 +2	281 ±2	30 days post last dose
Everyday Cognition Scale - Study Partner		X						X	X				X	X	
Neuropsychiatric Inventory - Caregiver Distress Scale		X					X		X	X			X		
Neuropsychological Test Battery	X	X					X		X	X		X	X		
Digit Symbol Substitution CCI	X	X					X		X	X		X	X		

Commercially Confidential Information

eCognitive At-Home Participant Assessment		2 times per week at baseline leading up to Day 1; 2 times per week in the week preceding Day 57; 2 times per week in the week preceding Day 85					

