If discontinuation from study treatment occurs, the investigator should make a reasonable effort to understand the primary reason for the participant's discontinuation from study treatment and record this information.

Participants who discontinue from study treatment will be considered discontinued from the study and will be asked to return for the Early Termination Visit indicated in the Assessment Schedule ([Table 8-1](#)).

If the participant cannot or is unwilling to attend the Early Termination Visit, the site staff should contact the participant, or participant's caregiver by phone.. This telephone contact should preferably be done according to the study visit schedule for Early Termination Visit.

At a minimum, the following data should be collected during the telephone contact:

- New / concomitant treatments
- Adverse Events / Serious Adverse Events

The investigator must also contact the IRT to register the participant's discontinuation from study treatment.

If discontinuation occurs because treatment code has been broken, please refer to Emergency breaking of assigned treatment code [Section 6.6.3](#).

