**Table 17-1 Key Information on canakinumab**

canakinumab	
Reference	IB
Drug type	Human monoclonal antibody
Half-life	26 days
Five half-lives	130 days
Generic name	Canakinumab
Formulation	Subcutaneous
Maximal planned clinical dose	300 mg q4 weeks
Target	Anti-human interleukin-1 $\beta$ (IL-1 $\beta$ ) antibody
Pharmacology	Blocks the interaction of IL-1 $\beta$ with the IL-1 receptor (IL-1R), leading to inhibition of its downstream targets, thereby preventing IL-1 $\beta$ -induced gene activation and the production of inflammatory mediators.

canakinumab	
Metabolism	Elimination pathways for the IgG-type mAbs such as canakinumab are distinct from metabolic pathways of small molecules. The IgG-based molecules are cleared from the body by a combination of processes such as proteolysis by the liver, elimination by the reticuloendothelial system (RES) and nonspecific endocytosis.
Potential to interact with other drugs based on in vitro studies	No study was conducted with canakinumab or its mouse surrogate, 1BSUR, to investigate drug-drug interaction in non-clinical species.
Reference safety information (RSI)*	System organ classes (SOCs) in the reference safety information tables as of the latest IB include infections and infestations across all indications below, in addition to the following:  CAPS: 

• Nervous system disorders

 Periodic fever syndromes 

• Investigations (platelet count decreased)

 SJIA: 

• Gastrointestinal disorders

• Immune system disorders

• Investigations (transaminases increased, platelet count decreased, neutrophil count decreased, white blood cell count decreased)

 Oncology: 

• Investigations (blood creatine phosphokinase increased)

• Blood and lymphatic system disorders

 Gouty arthritis and Cardiovascular risk reduction: 

• No additional SOCs

 Based on similarities of the patient population with Alzheimer's disease (including elderly, hypertensive, diabetes, cardiovascular disease, chronic obstructive pulmonary disease), the RSI Table 6-5 from the Cardiovascular risk reduction program (CANTOS) will be used as the RSI table for this study.

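### AE monitoring should run at least 130 days after the last canakinumab dose, but the visible schedule gives early stoppers no routine contact beyond about day 30

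*Protocol*

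**What the plan says.** - **Length of monitoring.** Protocol Section 10.1.1: "Adverse event monitoring should be continued for at least 30 days (or 5 half-lives or end of study visit, whichever is longer", counted from the last dose. In Table 17-1 the row "Five half-lives" reads 130 days, from a half-life of 26 days.
- **How events are found.** Section 10.1.1: "The occurrence of adverse events must be sought by non-directive questioning of the participant at each visit during the study". Participants may also volunteer events during or between visits.
- **Treated participants in general.** Section 4.5 says they "should have safety evaluations and collection of concomitant treatments and/or adverse event data until the predefined end of cohort date". It justifies the Day 281 visit (EOC2) on the ground that "20 weeks would be approximately 5 half-lives after last dose". For early discontinuation it refers the reader to Section 9.1.1.
- **Early stoppers.** Section 9.1.1: "Participants who discontinue from study treatment will be considered discontinued from the study and will be asked to return for the Early Termination Visit". Table 8-1 places that visit at "30 days post last dose". If the participant does not attend, Section 9.1.1 asks for a telephone contact, preferably on the same timing, and Section 9.4 says "a safety follow-up call will be conducted 30 days after last administration of study treatment".
- **Earlier contact.** Section 8 (study discontinuers) and Section 9.5 (sponsor termination) ask for a prompt final visit. Section 9.1.2 allows the final evaluation at the time of discontinuation.
- **Restrictions after dosing.** Table 17-4 bars live vaccines and TNF inhibitors until 130 days after dosing ends.

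**The concern.** The monitoring rule and the schedule meant to deliver it imply different durations for anyone who stops early. A site that follows the schedule exactly ends active questioning at about day 30, while the rule runs to at least day 130.

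The group affected includes participants who must stop for any SAE, a clinically significant infection (Section 9.1.1) or intolerance of the dose (Section 17.1.4.1). It also includes placebo participants and people who stop for reasons unrelated to safety. Infection, including serious and fatal infection, is among the safety risks selected in Table 17-1. After the last contact, a new infection, or a live vaccine given inside the barred period, comes to light only if someone volunteers it. These participants are cognitively impaired.

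There is a smaller reporting consequence. SAP Section 2.1.1 closes the on-treatment period at EOC1 or EOC2, and SAP Section 2.7.1 reports counts and percentages of participants with events. Early stoppers would probably contribute less observed time to those tables.

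**Working it through.** **Inputs.** Half-life 26 days (Table 17-1), range 21 to 30 days (Section 17.1.2.2.2); last routine contact 30 days after the last dose (Table 8-1, Section 9.4); six doses on Days 1, 29, 57, 85, 113 and 141; EOC2 on Day 281.

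**1. The plan's own figures.** 5 × 26 = 130 days, matching Table 17-1. For completers, 281 − 141 = 140 days = 20 weeks, as Section 4.5 states, and 140/26 = 5.4 half-lives. Completers therefore meet the rule at the 26-day half-life.

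**2. Shortfall for an early stopper = 5 × half-life − 30.**

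| Half-life (days) | Five half-lives | Days after a day-30 contact | Drug remaining at day 30 |
|---|---|---|---|
| 21 | 105 | 75 | 0.5^(30/21) = 37% |
| 26 | 130 | 100 | 0.5^(30/26) = 45% |
| 30 | 150 | 120 | 0.5^(30/30) = 50% |

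The last column assumes simple first-order decline. If the final contact falls before day 30, the shortfall grows by the same number of days.

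**3. In study days at 26 days.** For a last dose on Day 1, 29, 57, 85 or 113, the day-30 contact falls on Day 31, 59, 87, 115 or 143. Five half-lives end on Day 131, 159, 187, 215 or 243. The difference is 100 days each time.

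**4. Exceptions that shorten the gap (26-day half-life).**
- Missing more than two doses (Section 17.1.4.1): the third miss comes 28, 56 or 84 days after the last dose received. After three consecutive misses, at most 130 − 84 = 46 days remain.
- Anaphylaxis (Section 8.5.7): a sample 8 × 7 = 56 days after the event leaves 130 − 56 = 74 days if the event was on the day of the last dose.
- Antibody-positive at end of study (Section 8.5.7): 30 + about 90 = 120 days, leaving about 10. At the 0.5% to 2.9% incidence in Section 17.1.2.2.2, that is 0.005 × 43 = 0.2 to 0.029 × 43 = 1.2 of the 43 planned canakinumab participants (86/2).
- An adverse event already detected, a liver or renal event, pregnancy, or suspected hypersensitivity: follow-up depends on the event and has no fixed length.

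These contacts are prompted by a particular event or dosing history. None is a general, scheduled search for new events up to day 130.

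**The case against.** The best defence is that Section 10.1.1 is a standing duty on the investigator, and a visit table need not list every contact that the duty requires. Events can be volunteered between visits. Many reasons for stopping are themselves adverse events, which must be followed until they resolve or are judged permanent. Section 10.1.3 keeps suspected-related SAEs reportable after 30 days. The Cohort 1 module (Sections 17.1.1 and 17.1.13) names EOC2 as the end-of-study visit for participants randomized to the cohort, and the glossary entry for stopping treatment assumes continued follow-up. The site manual, the Safety Surveillance Plan and the redacted parts of Table 8-1 were not available.

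Much of this limits the point without removing it. A reader might infer that sites cannot comply; they can, by arranging contacts that the schedule does not list. A reader might also infer that most early stoppers lose exactly 100 days. The documents give neither the number of early stoppers nor the share with an exception, and the last contact may come before day 30. Nor do late related SAEs fall outside reporting; what is missing is a scheduled contact that would elicit them.

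What does not succeed is the appeal to EOC2. Section 9.1.1 treats people who stop treatment as out of the study and sends them to the Early Termination Visit. If Section 17.1.1 did govern them, Day 281 would be 168 to 280 days after a last dose on Day 113 to Day 1, and the Early Termination column gives no sign of that. Two possible readings of a safety duty are a reason to settle it in the text.

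**Conclusion.** The point holds as a gap between a stated monitoring period and the visible schedule. Unless an event-driven exception applies, an early stopper in the canakinumab cohort has no scheduled active search for new adverse events or prohibited treatments for about 100 days (75 to 120 over the stated half-life range), and longer if the final contact comes before day 30. This rests on taking Section 9.1.1 as governing early stoppers, and on no later contact being set out in the material not seen.

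It should be corrected, but it is not a threat to the trial's main result: the primary endpoint is unaffected. SAP Section 1.1 records that the study was terminated after 34 participants were randomized, so the remaining value is chiefly in core wording that later long-half-life cohorts would inherit.

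**What to change.** In Sections 9.1.1 and 9.4 and the Early Termination column of Table 8-1, for long-half-life cohorts, add one safety telephone contact at about five half-lives after the last dose (130 to 140 days for canakinumab). It should cover adverse events, SAEs and concomitant treatments, and include the study partner or caregiver where available.

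Apply it to every dosed participant who stops early, including under sponsor termination (Section 9.5). Exclude those who have withdrawn consent (Section 9.2 restricts contact) and those who have declined further follow-up without withdrawing consent (Section 9.1.2). Leave Section 10.1.3 unchanged: its 30-day limit on all-cause SAE reporting is a general rule that also applies to completers.

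The cost is protocol wording and one call per early stopper, with no added visit or procedure. The weakness is recall over about 100 days in people with cognitive impairment, some of whom stopped because they no longer had a study partner. At a 30-day half-life, a call at 130 to 140 days falls 10 to 20 days short of 150; EOC2, at 140 days, is 10 days short for completers too.

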### **10.1.2 Serious adverse events**

An SAE is defined as any adverse event (appearance of [or worsening of any pre-existing]) undesirable sign(s), symptom(s), or medical conditions(s) which meets any one of the following criteria:

- Fatal
- Life-threatening
  - Life-threatening in the context of a SAE refers to a reaction in which the participant was at risk of death at the time of the reaction; it does not refer to a reaction that hypothetically might have caused death if it were more severe (please refer to the

[\*\*International Conference on Harmonisation of Technical Requirements for Registration of Pharmaceuticals for Human 2003\).\*\*](#)

- Results in persistent or significant disability/incapacity
- Constitutes a congenital anomaly/birth defect
- Requires inpatient hospitalization or prolongation of existing hospitalization, unless hospitalization is for:
  - Routine treatment or monitoring of the studied indication, not associated with any deterioration in condition
  - Elective or pre-planned treatment for a pre-existing condition that is unrelated to the indication under study and has not worsened since signing the informed consent
  - Social reasons and respite care in the absence of any deterioration in the participant's general condition
  - Treatment on an emergency outpatient basis for an event not fulfilling any of the definitions of a SAE given above and not resulting in hospital admission
- Is medically significant, e.g. defined as an event that jeopardizes the participant or may require medical or surgical intervention to prevent one of the outcomes listed above

Medical and scientific judgment should be exercised in deciding whether other situations should be considered serious reactions, such as important medical events that might not be immediately life threatening or result in death or hospitalization but might jeopardize the participant or might require intervention to prevent one of the other outcomes listed above. Such events should be considered as "medically significant." Examples of such events are intensive treatment in an emergency room or at home for allergic bronchospasm, blood dyscrasias, or convulsions that do not result in hospitalization or development of dependency or abuse (please refer to the [\*\*International Conference on Harmonisation of Technical Requirements for Registration of Pharmaceuticals for Human 2003\).\*\*](#)

All malignant neoplasms will be assessed as serious under "medically significant" if other seriousness criteria are not met.

Any suspected transmission via a medicinal product of an infectious agent is also considered a serious adverse reaction.

All reports of intentional misuse and abuse of the product are also considered serious adverse event irrespective if a clinical event has occurred. Please see [\*\*Section 10.1.5\*\*](#) for more details.

